8.2.5. Days of Non-Invasive Ventilation/High-Flow Oxygen

Duration of non-invasive ventilation/high flow oxygen use will be summarized in a table using medians and quartiles by treatment arm. Analyses will be performed in the mITT and As Treated

populations. Bee swarm plots of non-invasive ventilation/high flow oxygen days by treatment arm will be generated, where subjects whose days are imputed to the maximum of 28 days due to death are grouped separately from subjects who do not die.

8.2.6. Incidence of New Non-Invasive Ventilation/High-Flow Oxygen

The incidence and duration of new Non-Invasive Ventilation/High-Flow Oxygen use will be analyzed by treatment arm. This will only include subjects in category 4 or 5 at randomization. New use will be identified by a post-randomization score of 6. The number of subjects reporting new use and the incidence rate (and CI) will be reported.

8.2.7. Days of Invasive Mechanical Ventilation/ECMO

Duration of Invasive Mechanical Ventilation/ECMO use will be summarized in a table using medians and quartiles by treatment arm. Analyses will be performed in the mITT and As Treated populations. Bee swarm plots of Invasive Mechanical Ventilation/ECMO days by treatment arm will be generated, where subjects whose days are imputed to the maximum of 28 days due to death are grouped separately from subjects who do not die.

8.2.8. Incidence of New Invasive Mechanical Ventilation/ECMO

The incidence and duration of new Invasive Mechanical Ventilation/ECMO use will be analyzed by treatment arm. New use will be identified by a post-randomization score of 7. The number of subjects reporting new use and the incidence rate (and CI) will be reported.

8.2.9. Days of Hospitalization

Duration of hospitalization will be summarized in a table using medians and quartiles by treatment arm. Incidence of readmittance will also be summarized ([Table 42](#)). Analyses will be performed in the mITT and As Treated population. Bee swarm plots of days hospitalized by treatment arm will be generated, where subjects whose days are imputed to the maximum of 28 days due to death are grouped separately from subjects who do not die.

8.3. Exploratory Efficacy Analyses

Analyses of exploratory outcome measures are not covered in this SAP.

9. SAFETY EVALUATION

9.1. Demographic and Other Baseline Characteristics

Summaries of age, sex, height, weight, BMI, ethnicity, and race will be presented by treatment group as well as geographic region, comorbidities, duration of symptoms prior to randomization, and disease severity ([Table 47](#) and [Table 48](#)). Ethnicity will be categorized as Hispanic or Latino, or not Hispanic and not Latino. In accordance with NIH reporting policy, subjects may self-designate as belonging to more than one race or may refuse to identify a race, the latter reflected in the CRF as “No” to each racial option.

Individual subject listings will be presented for all demographics and baseline characteristics ([Listing 7](#)).

9.1.1. Prior and Concurrent Medical Conditions

Focused medical history is obtained at the screening visit that includes the following:

- History of chronic medical conditions related to inclusion and exclusion criteria
- Review medications and therapies for this current illness.

Medical history is limited to the following conditions: asthma, cancer, cardiac valvular disease, chronic kidney disease, chronic liver disease, chronic oxygen requirement, chronic respiratory disease, coagulopathy, congestive heart failure, coronary artery disease, current nicotine consumption, diabetes I and II, hypertension, immune deficiency, and obesity. All current illnesses and past pre-existing medical conditions will be MedDRA® coded using MedDRA dictionary version 23.0 or higher. Summaries of subjects’ pre-existing medical conditions will be presented by treatment group ([Table 49](#)).

Individual subject listings will be presented for all medical conditions ([Listing 8](#)).

9.1.2. Prior and Concomitant Medications

Medication history (concomitant medications) includes a review of all current medications and medications taken within 7 days prior to enrollment through approximately Day 15 or early termination (if Day 15), whichever occurs first.

Summaries of medications that were started prior to dosing and continued at the time of dosing or started after dosing while on study will be presented by WHO Drug Level 1 and 2 Codes, disease severity, and treatment group ([Table 50](#)). Summaries of overall use of medications/therapies of interest listed in [Section 6.4](#) that were started prior to dosing and continued at the time of dosing or started after dosing while on study as well as use by select study days will also be generated ([Table 51](#) and [Table 52](#)).

Individual subject listings will be presented for all concomitant medications ([Listing 9](#)), corticosteroid use ([Listing 10](#)), and medications of interest ([Listing 11](#)).

9.2. Measurements of Treatment Compliance

Section 7 provides the descriptions of summaries of key treatment compliance milestones/variables. Individual subject listings will be presented for all subjects who discontinued dosing ([Listing 2](#)). Individual subject listings will be presented for all subjects who missed, halted or slowed any dose ([Listing 12](#)).

9.3. Adverse Events

For the calculation of incidence of adverse events (i.e., on a per subject basis), each subject will only be counted once and any repetitions of adverse events within a subject will be ignored; the denominator will be the number of subjects in the Treated population. All adverse events reported and treatment emergent will be reported in tables and listings; treatment emerge events are adverse events anytime following the initiation of administration with any study product (interferon beta-1a, remdesivir, or placebo). Select adverse event summaries will be replicated using the modified oxygen use scale.

An overall summary by treatment arm and disease severity of adverse events is presented that includes, but not limited to: subjects with at least one event, at least one related event, at least one SAE, at least one related SAE and at least one AE leading to early termination ([Table 53](#), [Table 54](#), [Table 55](#)).

Adverse events occurring in 5% of subjects (by MedDRA preferred term) in any treatment group will be presented ([Table 61](#), [Table 62](#), [Table 63](#)).

The proportion of subjects reporting at least one adverse event will be summarized by MedDRA system organ class and preferred term for each treatment arm, disease severity and overall. Denominators for percentages are the number of subjects in the Treated population.

The following summaries for adverse events will be presented by MedDRA system organ class, preferred term, disease severity and treatment group:

- Renal adverse events by preferred term ([Table 65](#), [Table 66](#));
- Hepatic adverse events by preferred term ([Table 67](#), [Table 68](#))
- Related adverse events by MedDRA system organ class and preferred term ([Table 69](#), [Table 70](#));
- Subject listing of non-serious adverse events ([Listing 13](#)) and listing of related adverse events ([Listing 14](#));
- Bar chart of non-serious related adverse events by severity and MedDRA system organ class ([Figure 28](#), [Figure 29](#));
- Bar chart of non-serious related adverse events by maximum severity and MedDRA system organ class ([Figure 30](#), [Figure 31](#)).

9.4. Deaths, Serious Adverse Events and other Significant Adverse Events

Serious adverse events will be summarized by MedDRA system organ class and preferring term ([Table 57](#), [Table 58](#), [Table 59](#)). Listings of death and other serious adverse events will be

presented, including Subject ID, treatment group, Adverse Event Description, Number of Days Post Dose (Duration), Number of Days Post Dose the Event Became Serious, Reason Reported as an SAE, Severity, Relationship to Treatment, Alternate Etiology if not Related, Action Taken with Study Treatment, Subject Discontinuation, Outcome, MedDRA SOC, and MedDRA PT ([Listing 15](#) and [Listing 16](#)).

The number of subjects who die by Day 15 and Day 29 will be presented by treatment arm. The 14- and 28-day mortality rate, which will use Kaplan-Meier estimator, will be presented ([Table 71](#), [Table 72](#), [Table 73](#), [Table 74](#)). Summaries will be provided for both the as-reported baseline ordinal score and the Modified Oxygen Use ordinal score described in Section [4.3](#).

Mortality through Day 15 and 29 will also be analyzed as a time to event endpoint (see Section [3.3](#)). A table will present median time to event along with 95% confidence intervals overall for each treatment arm along with the hazard ratio estimate and log rank p-values ([Table 75](#)). Differences in time-to-event endpoints by treatment will be summarized with Kaplan-Meier curves ([Figure 32](#)). Analyses of mortality will be performed in the mITT and the Treated analysis populations and will be replicated using the Modified Oxygen Use ordinal score described in Section [4.3](#). As a supplemental analysis, a Cox model will be fit with binary indicators for treatment group and disease severity as well as a treatment * disease severity interaction term. The model will be fit in the mITT and As Treated analysis populations. The treatment group hazard ratios and CIs and the interaction term p-value will be reported. Finally, the results of the subgroup and sensitivity time-to event analyses described in Section [6.4](#) will be presented in a table. A restricted mean survival time analysis of mortality will be performed as an exploratory analysis. The restricted mean mortality time estimates will be provided for each treatment group and randomized disease severity stratum as well as the difference in restricted mean recovery time between treatment groups within each of the severity strata ([Table 82](#)).

Analyses of the time to death or progression to invasive ventilation through Day 28 will be performed. Stratified (by baseline ordinal score) and subgroup (by baseline ordinal score) analyses will be performed ([Table 83](#), [Table 84](#)). The analysis will be repeated using the modified oxygen use scale. The analyses will also be replicated to explore time to death or progression to ventilation (non-invasive or invasive) through Day 28 ([Table 87](#), [Table 88](#), [Table 89](#)). These analyses will mirror those performed for the time to death outcome with the addition that the analyses will explore the outcome in the statin/ARB/AECI use subgroups.

Rates of Grade 3 and 4 AE occurrence will be summarized by treatment arm ([Table 90](#)). Rates of SAE occurrence will also be compared between treatment arms using Barnard's exact test and presented. Further, the composite endpoint of the occurrence of death, SAE, or Grade 3 or 4 AE described in Section [3.3](#) will be analyzed as a time to event outcome. A table will present median time to event along with 95% confidence intervals overall for each treatment arm along with the hazard ratio estimate and log rank p-values ([Table 91](#)). Differences in time-to-event endpoints by treatment will be summarized with Kaplan-Meier curves.

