Table 83: Time to Death or Progression to Invasive Ventilation through Day 28 by Treatment Group and Baseline Ordinal Score – mITT Population

Treatment Group	Baseline Ordinal Score	n	HR	
			Estimate	95% CI
Interferon beta-1a + RDV (N=X)	4	x	x.xx	x.xx, x.xx
Placebo + RDV (N=X)		x		
Interferon beta-1a + RDV (N=X)	5	x	x.xx	x.xx, x.xx
Placebo + RDV (N=X)		x		
Interferon beta-1a + RDV (N=X)	6	x	x.xx	x.xx, x.xx
Placebo + RDV (N=X)		x		
Interferon beta-1a + RDV (N=X)	Any Baseline Ordinal Score	x	x.xx	x.xx, x.xx
Placebo + RDV (N=X)		x		
Interferon beta-1a + RDV (N=X)	Any Baseline Ordinal Score (4 or 5)	x	x.xx	x.xx, x.xx
Placebo + RDV (N=X)		x		

NE = Not Estimated.

N= Number of subjects in the specified treatment group, baseline ordinal score, and analysis population.

n = Number of subjects who died or progressed to invasive ventilation by Day 28.

HR is the ratio of the hazard of death or progression to invasive ventilation in each treatment group estimated from the Cox model. The ratio is Interferon beta-1a + RDV to Placebo + RDV.

HR for the ‘Any Baseline Ordinal Score’ and ‘Any Baseline Ordinal Score (4 or 5)’ group is the hazard ratio from the stratified Cox Model.

Tables with similar format:

Table 84: **Time to Death Progression to Invasive Ventilation through Day 28 by Treatment Group and Baseline Ordinal Score – As Treated Population**

Table 85: **Time to Death Progression to Invasive Ventilation through Day 28 by Treatment Group and Baseline Modified Oxygen Use Ordinal Score – As Treated Population**

Table 86: **Time to Death or Progression to Non-Invasive or Invasive Ventilation through Day 28 by Treatment Group and Baseline Modified Oxygen Use Ordinal Score – mITT Population**

Table 87: **Time to Death or Progression to Non-Invasive or Invasive Ventilation through Day 28 by Treatment Group and Baseline Ordinal Score – mITT Population**

Table 88: **Time to Death or Progression to Non-Invasive or Invasive Ventilation through Day 28 by Treatment Group and Baseline Ordinal Score – As Treated Population**

Table 89: **Time to Death or Progression to Non-Invasive or Invasive Ventilation through Day 28 by Treatment Group, Baseline Ordinal Score, and Statin/ARB/AECI Use – mITT Population**

Programming Notes for Table 85 and Table 86:

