Figure 40: Kaplan-Meier Curve of Time to Death or Progression to Invasive Ventilation through Day 28 by Treatment Group – mITT Population, Baseline Ordinal Score of 5

Figure 41: Kaplan-Meier Curve of Time to Death or Progression to Invasive Ventilation through Day 28 by Treatment Group – mITT Population, Baseline Ordinal Score of 6

Figure 42: Kaplan-Meier Curve of Time to Death or Progression to Ventilation through Day 28 by Treatment Group – mITT Population

Figure 43: Kaplan-Meier Curve of Time to Death or Progression to Ventilation through Day 28 by Treatment Group – As Treated Population

Figure 44: Kaplan-Meier Curve of Time to Death or Progression to Ventilation through Day 28 by Treatment Group – mITT Population, Baseline Ordinal Score of 4

Figure 45: Kaplan-Meier Curve of Time to Death or Progression to Ventilation through Day 28 by Treatment Group – mITT Population, Baseline Ordinal Score of 5

Figure 46: Kaplan-Meier Curve of Time to Death or Progression to Ventilation through Day 28 by Treatment Group – mITT Population, Baseline Ordinal Score of 6

Figure 47: Kaplan-Meier Curve of Time to Death, SAE, or Grade 3 or 4 AE through Day 29 by Treatment Group – As Treated Population, Baseline Ordinal Score of 4 or 5

[figure not shown]
[figure not shown]

Figure with similar format:

Figure 48: Kaplan-Meier Curve of Time to Death, SAE, Discontinuation of Study Infusions or Grade 3 or 4 AE through Day 29 by Treatment Group – As Treated Population, Baseline Ordinal Score of 6

Figure 49: [Parameter X] Results by Scheduled Visits: Change from Baseline by Treatment Group – As Treated Population

Programming Note: The shell provided is a generic figure. The Groups within a panel will be treatment groups and the panels will be Baseline Ordinal Score (4, 5, or 6). The points will be the median change from baseline and the bars will represent the Q1 and Q3 quartiles of the change from baseline at each time point. Panels for each laboratory parameter will be generated.

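### For time to death or progression to non-invasive or invasive ventilation, the baseline score 6 and pooled results have no defined event or risk set; limit this endpoint to baseline scores 4 and 5

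*SAP*

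**What the plan says.** SAP 9.4 plans an analysis of death or progression to invasive ventilation through Day 28, for which "Stratified (by baseline ordinal score) and subgroup (by baseline ordinal score) analyses will be performed". It then widens the event: "The analyses will also be replicated to explore time to death or progression to ventilation (non-invasive or invasive) through Day 28". It adds that "These analyses will mirror those performed for the time to death outcome"; the time-to-death shell, Table 75, has rows for scores 4, 5 and 6, a pooled row and a 4-or-5 row.

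The outputs for the wider event are in SAP Appendices 1 and 2:

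- **Tables 86 to 88** are listed as similar in format to Table 83, whose rows are baseline score 4, 5, 6, a pooled row (Any Baseline Ordinal Score) and a 4-or-5 row. Table 87, for example, is titled "Time to Death or Progression to Non-Invasive or Invasive Ventilation through Day 28 by Treatment Group and Baseline Ordinal Score – mITT Population". The only programming note for Table 86 adds a footnote on the modified oxygen scale. Tables 87 and 88 have no note.
- **Figures 42 and 43** pool all baseline scores. Figures 44 and 45 take scores 4 and 5. Figure 46 is the Kaplan-Meier curve of "Time to Death or Progression to Ventilation through Day 28 by Treatment Group – mITT Population, Baseline Ordinal Score of 6".
- **Table 89**, the same event by statin/ARB/ACE-inhibitor use, is limited by its programming note to baseline scores 4 and 5.

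SAP 3.2 defines score 6 as hospitalized on non-invasive ventilation or high-flow oxygen. SAP 3.3 defines the other time-to-event endpoints but not this one.

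**The concern.** A time-to-event analysis needs patients who are free of the event at the start. Ventilation, including non-invasive ventilation, is part of this event, and non-invasive ventilation is part of what defines score 6. Some or all score 6 patients therefore start in the state that the endpoint is meant to detect, and the SAP has no rule for them. A programmer following the shells would have to choose one, and the output would not show which choice was made.

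At stake are the score 6 row, the pooled row, and Figures 42, 43 and 46. Score 6 is the stratum that the DSMB closed to enrolment on September 4, 2020, so readers will look at those results closely.

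**Working it through.** The plan gives no figure to reproduce. The check compares the event with the rows and figures planned for it.

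**1. How ventilation status is ascertained.** SAP 4.3 says that ventilation and high-flow use are assessed from the 8-point scale and post-discharge questions. SAP 3.3.6 counts non-invasive ventilation/high-flow days as days at score 6. Protocol Appendix C, 8.1.2.1, records the non-invasive ventilation and high-flow requirements as separate items, so a device-based event is also possible.

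**2. What each reading does to baseline score 6.**

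| Reading of the event | Score 6 at baseline | Score 6 row | Pooled row |
|---|---|---|---|
| Score-based: score 6, 7 or death | all in the event state | no treatment information | diluted toward 1 |
| Worsening only: score 7 or death for those at 6 | at risk of a different event | repeats Table 83 | mixes two endpoints |
| Device-based: non-invasive or invasive ventilation, or death | in the event state only if already on non-invasive ventilation | interpretable only if those patients are removed | as the score 6 row |

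No reading puts a patient with baseline score 4 or 5 in the event state at randomization, so the 4-or-5 row has a sound risk set.

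**3. What the SAP does elsewhere.** New oxygen use is limited to category 4 (8.2.4). For new non-invasive ventilation/high-flow oxygen, "This will only include subjects in category 4 or 5 at randomization" (8.2.6). The new-use section is dropped from the score 6 tables (Tables 34 and 37). Patients who enter with NEWS of 2 or less must be discharged to meet that endpoint (3.3.5). Table 89 applies the 4-or-5 limit to this very event.

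**4. Size under the score-based reading (illustration).** Suppose all n patients in the score 6 stratum, n1 treated and n0 control, have the event at the first time point. The Cox score equation for that stratum is n1 = n × n1·HR/(n1·HR + n0). With n = n1 + n0 this gives HR = 1 whatever the treatment does. In a stratified Cox model with Breslow or Efron ties, the stratum therefore acts like n extra events with log HR of 0.

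The inputs below are assumptions, not figures from the documents: 870 patients at score 4 or 5 (435 per arm), a 15% control event rate by Day 28, and a true HR of 1.5.

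- Control events: 435 × 0.15 = 65.3
- Treated events: 435 × (1 − 0.85^1.5) = 435 × 0.216 = 94.1
- Total: 159.4

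With balanced arms, each event carries roughly equal weight, so pooled log HR ≈ ln(1.5) × 159.4/(159.4 + n), with ln(1.5) = 0.405.

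| Score 6 patients (n) | Pooled log HR | Pooled HR | Simulated pooled HR (200 replicates; Efron, Breslow) |
|---|---|---|---|
| 25 | 0.351 | 1.42 | 1.41, 1.43 |
| 50 | 0.309 | 1.36 | 1.36, 1.38 |
| 100 | 0.249 | 1.28 | 1.28, 1.29 |

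Under exact handling of ties, an all-tied stratum contributes nothing and the pooled HR equals the 4-or-5 HR. The Cox pseudocode in SAP 6.1 names no ties method.

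**The case against.** The strongest reply is that the endpoint names ventilation only. Score 6 also covers high-flow oxygen, and where the SAP means both it names both, as in the headings of 8.2.5 and 8.2.6. The protocol records the two devices separately and says in Appendix C, 9.2, that the scale's elements are captured separately to allow other groupings. On that wording, a score 6 patient on high-flow oxygen alone is still at risk. This stands. A reader might infer that every score 6 patient is an event at time zero; the documents do not support so general a statement. They give neither the split between devices nor a definition that settles the matter.

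It also stands that 8.2.6 is not a like-for-like precedent. Its event is score 6 itself, so its exclusion follows by definition. Table 89 is the better precedent, because it concerns the same event.

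Progression ordinarily means worsening, so counting everyone as an event at baseline is the least natural reading. But if score 6 patients are scored on reaching 7 or dying, their row repeats Table 83 and the pooled row joins two endpoints.

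Finally, the analysis is exploratory, the Table 83 format has no p-value column, and the endpoint is outside the list in SAP 6.8 whose p-values depend on the primary result. Those facts limit the importance of the point. They do not supply the missing definition.

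**Conclusion.** The point holds, as a minor one. Tables 86 to 88 and Figures 42, 43 and 46 include score 6 patients, alone or pooled, for an event that some or all of them have already met. Under score-based ascertainment all of them have; under a device-based reading only those on non-invasive ventilation have. Because the SAP defines neither the event nor the risk set, the score 6 and pooled hazard ratios are uninformative or combine two endpoints.

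The dilution to about 1.42, 1.36 or 1.28 rests on assumed patient numbers and event rates and on the score-based reading. It shows the direction and possible size, not a forecast. A reader might also infer that the trial's conclusions or the safety assessment of score 6 are compromised. They are not: the primary and key secondary analyses do not use this endpoint, and score 6 remains covered by death or invasive ventilation, mortality and adverse events.

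**What to change.** Make the 4-or-5 analysis the overall result for this endpoint:

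- Restrict Tables 86 to 88 and Figures 42 and 43 to baseline scores 4 and 5, and drop the score 6 and pooled rows.
- Delete Figure 46, which contains only score 6 patients and so cannot be restricted.
- Add a short definition to SAP 3.3 stating the event and who is at risk. It should say whether a move to high-flow oxygen alone counts, since that affects the event count at scores 4 and 5 as well.

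Score 6 stays covered by death or invasive ventilation (Tables 83 to 85 and Figure 41). If a score 6 analysis of the wider event is wanted, define the event by device from the separately recorded items and exclude patients already on non-invasive ventilation at baseline.

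The cost is a few shell edits and a sentence or two of text, with no new data collection. The loss is one exploratory score 6 row and its figure.
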